1.0 REVISION HISTORY

Revision #	Date	Description
01	28 February 2022	Initial release
02	09 May 2022	Made cardiac enzymes optional to align with standard of care myocardial infarction diagnosis, added additional GDPR data privacy information, added Clinical Trial Agreement wording, changed “patient” and “subject” terminology to “participant” to align with EU terminology

2.0 SYNOPSIS

Study Sites	Up to 10 study sites will participate in this study
Study Objective	Demonstrate the safety and performance of the LiquID Guide Catheter Extension
Study Device	LiquID Guide Catheter Extension (LiquID)
Study Design	Single arm, open label, historically controlled, multicenter study evaluating the primary safety and performance endpoints
Study Duration	The study is expected to take approximately 6-9 months to enroll. Follow-up will consist of evaluation through patient discharge and a 7-10 day phone follow-up to assess for adverse events.
Primary Endpoint	
In-hospital major adverse cardiac events (MACE), defined as any of the following events that occur within 48 hours post-procedure, or through patient discharge, whichever occurs first:
 
 • Device-caused events including: 
 ◦ Target vessel dissection ◦ Longitudinal stent deformation ◦ Proximal collar stent stripping • Cardiac death • Stroke • Peri-procedural myocardial infarction (MI) based on participant symptoms, ECG changes and/or SCAI definition¹ (if cardiac enzymes are available) 
The primary endpoint for each patient in the Safety Population is the presence/absence status for any MACE as defined above.

Primary Performance (Effectiveness) Endpoint	Device Oriented Clinical Outcome (DOCE), defined as successful deployment and retrieval of the LiquID device without any device deficiencies or where use of the LiquID device directly leads to a MACE, target vessel dissection, longitudinal stent deformation or proximal collar stent stripping.
Inclusion Criteria Participants must be:	
 1. scheduled for non-emergent, percutaneous coronary procedure in which the use of a guide catheter extension is anticipated 2. able to provide informed consent to participate in the study

Clinical Exclusion Criteria Participants must not have:	
 1. evidence of ongoing ST-elevation myocardial infarction (STEMI) or STEMI treatment for late presentation STEMI with index admission (stabilized acute coronary syndrome allowed) 2. left ventricular ejection fraction <20% 3. required intervention in a saphenous vein graft 4. an intolerance or known allergy to medications/contrast expected to be used during the procedure or during hospital stay 5. had a cardiac intervention within two weeks of the procedure 6. renal insufficiency (serum creatinine of > 2.3 mg/dl) 7. active gastrointestinal bleeding 8. an active infection or fever (>37.8° C) that may be due to infection 9. significant anemia (hemoglobin < 8.0 mg / dl) 10. severe uncontrolled systemic hypertension (systolic press. > 240 mm Hg within the past month) 11. a severe electrolyte imbalance 12. congestive heart failure (NYHA Class IV) 13. presented with an acute coronary syndrome where serum troponin concentrations have not been demonstrated to be declining prior to the scheduled procedure (within the past two weeks) 14. uncontrolled diabetes (> 2 serum glucose concentrations of > 350 mg/dl within the past 7 days) 15. participation in an investigational protocol 16. unwillingness or inability to comply with any protocol requirements 17. angina, or ischemia caused by occluded artery 18. other clinical conditions, that in the opinion of the investigator significantly compromise the ability to perform a safe and/or effective procedure
Vulnerable Population Exclusion Criteria Participants must not be:	
 1. under 18 years old 2. pregnant or nursing 3. immuno-compromised 4. over 89 years old 5. incapacitated, mentally compromised or otherwise incapable of understanding and/or providing informed consent (including emergency situations)
Data Collection	
Screening
 
 a. Demographics (e.g., age, sex, race) b. Documentation of disease-related characteristics c. Previous and current treatments for disease d. Baseline (pre-procedure) cardiac enzymes 
Procedure
 
 a. Duration (1st sheath in, to the last sheath out/participant leaving cath lab) b. Device-Oriented Clinical Outcome (DOCE) c. Procedure-Oriented Clinical Outcome (POCE) d. Device deficiencies/malfunctions e. Adverse events/adverse device effects f. Procedure usability data 
Follow-up (48 hours/patient discharge & 7-10 day phone call)
 
 a. Assessment for adverse events/adverse device effects b. Cardiac enzymes at 1 hour (± 15 min) and 4-6 hours post-procedure

Sample Size	
Based on historical data regarding the event rate in the safety outcome^{2,3,4,5}, an exact binomial calculation was used to estimate sample size with the following assumptions⁶:
 
• Wilson score 95% confidence level (CL) for study MACE incidence rate, i.e. 1-sided $\alpha = (1-CL)/2 = 0.025$• True underlying MACE incidence rate = 0.02 (2% MACE rate)• Delta factor = 0.08, i.e., the goal is to reject 0.10, or a 10% MACE incidence rate, at a 1-sided p of 0.025 significance level 
A sample size of 85 evaluable participants is proposed based on the above assumptions. In order to reject a true MACE incidence rate of 10% at a 1-sided α level of 0.025, at most 3 out of 85 participants (3.5%) can have MACE in the study. The actual α level is 0.0245 if the true MACE incidence rate is 10%; the power is 0.91 if true MACE incidence rate is 2%. Assuming a 10% attrition rate, 95 participants will be enrolled.

Study Committees	Due to the relatively small size of the study, no study committees will be used but an independent medical monitor cardiologist will be used to adjudicate events and provide safety oversight for the study.

3.0 INTRODUCTION

3.1 Background

Cardiovascular disease (CVD), including coronary heart disease (CHD), is a common ailment caused by the accumulation of atherosclerotic plaque in the arteries of the body. According to the European Heart Network⁷, CVD causes 3.9 million deaths in Europe (1.8 million in the EU) and accounts for 45% of all deaths in Europe (37% in the EU). The total prevalence of CHD in the United States is 6.7% in adults over 20 years of age with a prevalence of myocardial infarction (MI) of 3.0%.⁸ CHD may be impacted by factors such as family history (inherited/genetic component), diet, physical activity level, stress (lifestyle components), and regular medical screenings and/or follow-up (awareness/maintenance components).

Procedure History

The most common treatment of CHD is percutaneous coronary intervention (PCI), typically with stent placement, occurring at rates of 95-386/100,000 of the general population in the EU. Coronary artery bypass graft (CABG) surgery also remains a treatment option but typically for more complex procedures. Its use has been declining in recent years (18-73/100,000) as new tools and techniques emerge in PCI.⁸ Among these new tools is a category called guide catheter extensions. These include devices such as the Guideliner (Teleflex), the Guidezilla (Boston Scientific), and the Telescope (Medtronic).

Device History

The LiquID 061 and LiquID 071 Guide Catheter Extensions (LiquID) are new, unique guide extension devices that optimize compatibility by working with a wider range of sizes of both guide catheters and therapeutic delivery catheters.

3.2 Alternative Treatments and Methods

As mentioned above, other guide catheter extension devices are already on the market in the EU, so those devices may be used as an alternative. Procedures may also be performed without the use of guide catheter extensions. Procedures that cannot be treated via PCI may be treated with CABG procedures.

3.3 Rationale for Procedure/Device

The wider range of device compatibility of LiquID potentially allows guide catheter extension device use in a wider range of clinical conditions (e.g., vessel size, tortuosity, etc.)

3.4 Previous Clinical Experience

This study will be the first clinical use of the LiquID devices.

4.0 STUDY OVERVIEW

4.1 Study Design

The study is a non-randomized, open label study at up to 10 clinical sites. The sites identified are anticipated to be the following:

- Royal Edinburgh, [name] – [name]
- Golden Jubilee National Hospital, [name] – [name]
- St. George's Hospital, [name] – [name]
- University Hospitals Bristol, Trust Headquarters, [name] – [name]
- Spire Cardiff Hospital, [name] – [name]
- Mater Private Hospital, [name] – [name]
- Galway University Hospital, [name] – [name]
- Ziekenhuis Oost-Limburg, [name] – Prof. dr. [name]
- Additional sites to be determined

Up to 95 participants will be enrolled but enrollment will be stopped as soon as data from 85 clinical procedures using the LiquID devices are obtained.

4.2 Study Objectives

The purpose of this study is to provide initial clinical evidence to establish the safety and performance of the LiquID Guide Catheter Extension in support of post-market clinical follow-up (PMCF) the device for use in PCI.

4.2.1 Primary Endpoint

In-hospital major adverse cardiac events (MACE), defined as any of the following events that occur within 48 hours post-procedure, or through participant discharge, whichever occurs first:

- Device-caused events including:
 - Target vessel dissection
 - Longitudinal stent deformation
 - Proximal collar stent stripping
- Cardiac death
- Stroke
- Peri-procedural myocardial infarction (MI) based on participant symptoms, ECG changes, or SCAI definition¹ (if cardiac enzymes are available)

The primary endpoint for each participant in the Safety Population is the presence/absence status for any MACE as defined above.

4.2.2 Secondary Endpoints

Device Oriented Clinical Outcome (DOCE), defined as successful deployment and retrieval of the LiquID device without any device deficiencies or where use of the

LiquID device directly leads to a MACE, target vessel dissection, longitudinal stent deformation or proximal collar stent stripping.

5.0 STUDY POPULATION

5.1 General Considerations

Patients who are scheduled for percutaneous intervention to treat coronary artery disease who do not have significant comorbidities that might confound outcomes will be considered for enrollment in this trial. Due to the short follow-up and relatively inclusive selection criteria in this trial, recruitment for this trial should be straightforward.

Up to 95 participants will be enrolled in the trial in order to generate data for 85 cases in which the LiquID devices are used clinically. A participant is considered enrolled when they meet study enrollment (all inclusion and no exclusion) criteria and have signed informed consent. All enrolled participants will be assigned a study ID consisting of a 2-digit site number and a 3-digit sequential participant number (e.g., 01-005).

5.2 Informed Consent

The process for obtaining informed consent will be subject to requirements specific to each clinical site but in general the patient will be approached by study site personnel about potential participation in the study. A copy of the informed consent form will be provided to the patient for their review. The patient will be given time to consider participation in the study and will be provided the opportunity to ask questions of regarding their participation in the trial. No indirect forms of informed consent will be allowed in this study, including but not limited to consent provided by a legal representative, spouse, legal guardian, or other advocate in the event that the patient cannot provide informed consent directly. The patient must sign the informed consent form. For patients that do not speak the local language a translated consent form may be provided at some participating sites. Alternatively, a translator may be provided to explain the study and the consent process as allowed by local regulations and/or clinical site policy.

5.3 Inclusion Criteria

Participants must be:

1. scheduled for non-emergent, percutaneous coronary procedure in which the use of a guide catheter extension is anticipated
2. able to provide informed consent to participate in the study

5.4 Clinical Exclusion Criteria

Potential participants must not have:

1. evidence of ongoing ST-elevation myocardial infarction (STEMI) or STEMI treatment for late presentation STEMI with index admission (stabilized acute coronary syndrome allowed)
2. left ventricular ejection fraction <20%
3. required intervention in a saphenous vein graft

4. an intolerance or known allergy to medications/contrast expected to be used during the procedure or during hospital stay
5. had a cardiac intervention within two weeks of the procedure
6. renal insufficiency (serum creatinine of > 2.3 mg/dl)
7. active gastrointestinal bleeding
8. an active infection or fever (>37.8° C) that may be due to infection
9. significant anemia (hemoglobin < 8.0 mg / dl)
10. severe uncontrolled systemic hypertension (systolic press. > 240 mm Hg within the past month)
11. a severe electrolyte imbalance
12. congestive heart failure (NYHA Class IV)
13. presented with an acute coronary syndrome where serum troponin concentrations have not been demonstrated to be declining prior to the scheduled procedure (within the past two weeks)
14. uncontrolled diabetes (> 2 serum glucose concentrations of > 350 mg/dl within the past 7 days)
15. participation in an investigational protocol
16. unwillingness or inability to comply with any protocol requirements
17. angina, or ischemia caused by occluded artery
18. other clinical conditions, that in the opinion of the investigator significantly compromise the ability to perform a safe and/or effective procedure

5.5 Vulnerable Population Exclusion Criteria

Potential participants must not be:

1. under 18 years old
2. pregnant or nursing
3. immuno-compromised
4. over 89 years old
5. incapacitated, mentally compromised or otherwise incapable of understanding and/or providing informed consent (including emergency situations)

[figure not shown]
6.0 DEVICE DESCRIPTION

6.1 General Description

The LiquID Guide Catheter Extensions are a single lumen catheter offered in a 6F (LiquID 061) and 7F (LiquID 071) size. The 150cm device has a stainless-steel shaft connected to a 15cm single lumen tube, which is used to extend traditional guide catheters. The 15cm single lumen tube catheter body contains a coil for kink resistance and radiopacity. The single lumen tube catheter body is also silicone coated for lubricity. The device has two

proximal positioning marks located at 95cm and 105cm from the distal tip. The device handle is color coded to match the standard guide catheter color code.

Figure 1: 6F Device Image (.068 in dimension is the outer diameter)

6.2 Intended Use

The LiquID Guide Catheter Extension is intended to be used in conjunction with guide catheters to access discrete regions of the coronary and/or peripheral vasculature, and to facilitate placement of interventional devices.

6.3 Claims and Intended Performance Verification

This study is intended to support claims that the LiquID devices are safe and effective for their intended use.

6.4 Number of Devices

Most procedures will require one device per case but occasionally an additional device may be required. It is conservatively estimated that 1.3 devices per case will be required for a total of 95 devices used in 85 evaluable cases.

6.6 Principle of Operation

The LiquID devices support the delivery of interventional devices by allowing more distal access of coronary and peripheral arteries. Passing the device beyond the distal tip of the guide catheter and into the vessel improves guide catheter back-up support thus improving the ability to push subsequent devices beyond points of obstruction. In addition, the guide catheter extension may itself cross points of obstruction allowing direct delivery of interventional devices to mid or distal portions of vessel anatomy.

Device operation includes introduction through a previously placed coronary or peripheral guide catheter and into a position within the target vessel using common interventional cardiology techniques. Subsequent devices are delivered in parallel to the LiquID push rod, through the interior lumen of the LiquID catheter body and into the target vessel beyond the distal tip.

7.0 PRE-PROCEDURE EVALUATION

7.1 Pre-Procedure Tests/Data

- a. Demographics (e.g., age, gender, race)
- b. Documentation of disease-related characteristics
- c. Previous and current treatments for disease

8.0 CLINICAL PROCEDURE

All study procedures will be performed according to the study site's standard of care. No special procedures or tests are required for this protocol.

8.1 Device Preparation, Introduction, and Use

The LiquID devices and all other devices to be used in the study procedure will be prepared according to their product instructions for use (IFU).

8.2 Perform Procedure

All study procedures will be performed per the clinical study site's standard of care. Seigla Medical personnel may be present during study procedures, but they are not required to be at all study cases.

8.3 Procedure Data

- a. Procedure Duration, measured as the time from the introduction of the first sheath into the participant, to the last sheath removed from the participant. If a sheath is left in the participant post-procedure, the procedure time will end when the participant leaves the catheter laboratory (cath lab).
- b. Device Oriented Clinical Outcome (DOCE), defined as the successful deployment and retrieval of the LiquID device without any device deficiencies or where use of the LiquID device directly leads to a MACE, target vessel dissection, longitudinal stent deformation or proximal collar stent stripping.
- c. Procedure Oriented Clinical Outcome (POCE), defined as DOCE without any device- or procedure-related event (causal or probable) that leads to a MACE.
- d. The occurrence of any device deficiencies/malfunctions
- e. The occurrence of any adverse events/adverse device effects

9.0 POST-PROCEDURE CARE/STUDY EVALUATIONS

Participant assessments will consist of an evaluation at 48 hours post-procedure or through participant discharge, whichever occurs first, and a follow-up telephone call 7-10 days post-procedure. At those evaluations, the following will be followed/assessed:

9.1 Post-Procedure Tests & Assessments

- a. Cardiac enzymes at 1 hour (± 15 minutes) and 4-6 hours post-procedure
- b. Assess for the occurrence of adverse events/adverse device effects
- c. All other participant care post-procedure during the study will be according to the clinical study site's standard of care.

9.2 Participant Care Following the Investigation

Following the participant's involvement in the clinical investigation, there will be no special care provided. Participant care following the investigation will be exactly the same as it would be if they were not in the study.

10.0 STATISTICAL METHODS

10.1 Sample Size Estimation

For the primary endpoint of participant incidence of any MACE, the rates in similar prior studies²⁻⁵ provided information to establish an estimated rate for this study of 2.0%. The exact binomial probability calculation was used to determine the sample size, using the following assumptions⁶:

- 95% confidence level (CL) for study MACE incidence rate, i.e., 1-sided $\alpha = (1-CL)/2 = 0.025$
- True underlying MACE incidence rate = 0.02 (2% MACE rate)
- Sampling delta factor = 0.08, i.e., performance goal to reject = 0.10, or 10%, at a 1-sided p of 0.025 significance level

A sample size of 85 evaluable participants is proposed based on the above assumptions. In order to reject a true MACE incidence rate of 10% at a 1-sided α level of 0.025, at most 3 out of 85 participants (3.5%) can have a MACE in the study. The actual α level is 0.0245 if the true MACE incidence rate is 10% and the power is 0.91 if true MACE incidence rate is 2%

Allowing for attrition, including cases in which the study device is not used and participants that are not available for follow-up assessments, up to 95 participants may be enrolled to obtain 85 evaluable cases.

10.2 Analysis Populations

10.2.1 Primary Endpoint (Safety) Population

The population for the primary endpoint will be any participant into whom the study device is introduced, regardless of whether or not it is used as intended.

10.2.2 Secondary Endpoint (Performance) Population

The population for the secondary endpoint will be participants into whom the study device is introduced and used as intended.

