10.3.3 Performance Analysis

For the Performance Population, the proportion of participants achieving the composite secondary endpoint of Device Oriented Clinical Outcome (DOCE), defined as the successful deployment and retrieval of the LiquID device without any device deficiencies or where use of the LiquID device directly leads to a MACE, target vessel dissection, longitudinal stent deformation or proximal collar stent stripping, will be reported with a 95% confidence interval. In addition, the proportions of (a) participants achieving each component of DOCE, (b) participants achieving POCE, and (c) study device that malfunctioned will be similarly reported.

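### The DOCE denominator depends on a condition judged after introduction and not defined in the available text; one reading would let failed deployments drop out

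*Combined protocol and SAP*

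**What the plan says.** The plan has two analysis populations. The Safety Population (section 10.2.1) is "any participant into whom the study device is introduced, regardless of whether or not it is used as intended". For the Performance Population, section 10.2.2 reads: "The population for the secondary endpoint will be participants into whom the study device is introduced and used as intended".

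Section 10.3.3 computes DOCE in the Performance Population, with a 95% confidence interval. DOCE is "defined as the successful deployment and retrieval of the LiquID device without any device deficiencies", and the sentence then continues "or where use of the LiquID device directly leads to a MACE" and lists vessel-dissection and stent-damage events. The same section plans the proportion of "participants achieving each component of DOCE" and the proportion achieving POCE. Item (c) concerns the "study device that malfunctioned will be similarly reported".

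The nearest text to a definition of intended use is section 6.2, which says that the device is "intended to be used in conjunction with guide catheters to access discrete regions of the coronary and/or peripheral vasculature" and is to facilitate placement of interventional devices. That describes the product. It does not give a rule for classifying a participant.

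DOCE is listed as a secondary endpoint in section 4.2.2 and as the primary performance endpoint in the synopsis (section 2.0).

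**The concern.** Successful deployment and retrieval are part of what DOCE measures. A denominator that depends on how the device was used after introduction can therefore overlap with the outcome. Sections 10.2.1 and 10.2.2 together show that the plan expects some introduced devices not to be used as intended, and that it removes those participants from the performance set only. If a device that would not reach position, or was withdrawn, is classed as not used as intended, a DOCE failure is taken out of the calculation instead of being counted.

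The available sections name no rule, assessor or time point for this classification. Section 13.7 gives the Medical Monitor event adjudication and safety oversight, not population membership. Two analysts could therefore report different DOCE rates from the same data. This matters because section 6.3 uses the study to support effectiveness claims, and because the study is single-arm and open-label. A rule fixed in advance is then the main protection against selective classification.

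**Working it through.** **Step 1. Readings of the condition in 10.2.2.**

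- Reading B: the device was used for its stated purpose (section 6.2). A failed deployment was still an attempt at intended use, so it stays in as a DOCE failure. The shift is 0.
- Reading A: the device did what it was meant to do. A device introduced and then failed or abandoned is excluded. The DOCE, component and POCE proportions rise.

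Section 10.2.1 uses the same phrase without explaining it, so it does not settle the choice.

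**Step 2. Would another planned output show the excluded cases?** Section 10.3.3 plans no DOCE result for all introduced participants. Table (d) in section 10.3.2 covers discontinuation of the device because of an adverse event, so it misses a device abandoned without one. Item (c) in section 10.3.3 counts malfunctioning devices, but its denominator is not stated. If it covers all devices, failures due to malfunction stay visible even under reading A. The gap that remains for certain is a device abandoned with neither a malfunction nor an adverse event.

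**Step 3. Check of the interval method.** The plan gives no figure for DOCE. Its only interval is the Wilson 95% interval for MACE at 3/85 in section 10.3.2. With p = x/n and z = 1.96:

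- centre = (p + z²/2n) / (1 + z²/n)
- half-width = z √[p(1 − p)/n + z²/4n²] / (1 + z²/n)

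For 3/85 this gives 1.2% to 9.9%, as the plan states.

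**Step 4. Size under reading A.** Inputs: n = 85 introductions, taking the 85 evaluable participants of section 10.1 as introductions (an assumption, since sections 4.1 and 5.1 count cases in which the device is used); f = failed or abandoned deployments excluded (assumed, because the documents give no failure rate); g = other DOCE failures that stay in (assumed). Successes are s = n − f − g.

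- All introduced: s/n
- Filtered: s/(n − f)
- Shift: s/(n − f) − s/n = s·f / [n(n − f)], which reduces to f/n when g = 0

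| f | g | All introduced (Wilson 95% CI) | Filtered (Wilson 95% CI) | Shift, points |
|---|---|---|---|---|
| 0 | 0 | 85/85 = 100% (95.7–100) | 85/85 = 100% (95.7–100) | 0 |
| 1 | 0 | 84/85 = 98.8% (93.6–99.8) | 84/84 = 100% (95.6–100) | 1.2 |
| 4 | 0 | 81/85 = 95.3% (88.5–98.2) | 81/81 = 100% (95.5–100) | 4.7 |
| 8 | 0 | 77/85 = 90.6% (82.5–95.2) | 77/77 = 100% (95.2–100) | 9.4 |
| 4 | 4 | 77/85 = 90.6% (82.5–95.2) | 77/81 = 95.1% (88.0–98.1) | 4.5 |

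The last row by the formula: 77 × 4 / (85 × 81) = 308/6885 = 4.5 points. The two rates in a row share participants, so the intervals show scale only and should not be compared by overlap.

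**Step 5. The DOCE sentence.** Read literally, the clause beginning with "or" joins device-caused events to the description of success. The sense must be that such events are failures. The sentence appears in sections 2.0, 4.2.2, 8.3 b and 10.3.3.

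**The case against.** The strongest reply is that reading A is the weaker one. The phrase concerns how the device was used, not how it performed. Section 6.2 is headed as intended use, and section 6.3 seeks claims limited to it, so a performance set restricted to intended use fits the claim. Reporting each DOCE component would have little purpose if failed deployments were already excluded, because the deployment component would be close to 100% by construction. This stands: reading B is the more natural one, and under it nothing is biased. It does not close the point, because the text does not exclude reading A for a device introduced and then withdrawn.

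It can also be said that a definition may sit in the section between 6.4 and 6.6 or in the instructions for use, neither of which was available. That stands as a limit: the claim is only that the available sections contain none.

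A third reply is that no decision changes. Section 10.3.1 makes performance descriptive, section 10.3.3 sets no threshold, and the only success rule, for MACE, uses every introduced participant. That is correct and limits the weight of the point.

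Finally, defining the phrase and naming who applies it would resolve the ambiguity without changing the main denominator. That would be an acceptable minimum. The Safety Population is still the better main denominator: it already exists and needs no judgement after introduction, and the intended-use question can be kept as a supplementary analysis.

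**Conclusion.** The point holds in a limited form and should be fixed. Section 10.2.2 applies to DOCE an exclusion judged after introduction and not defined in the available sections, and section 10.3.3 plans no DOCE result for all introduced participants. Bias is possible, not shown. It is 0 under the more natural reading. Under the other reading, with 85 introductions and no other failures, 4 exclusions change 95.3% to 100%, a shift of 4.7 points. Every failure count is assumed.

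A reader might infer three stronger conclusions that the documents do not support:

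- That the plan does remove failed deployments. The wording permits this but does not require it, and section 6.2 and the component reporting point the other way.
- That the malfunction proportion is biased too. Item (c) counts devices, its denominator is not stated, and the closing words may mean only that an interval is given.
- That the shift could reach 10.5 points: 85/85 against 85/95 = 89.5%, using all 95 − 85 = 10 spare places. This equates cases in which the device is used (sections 4.1 and 5.1) with cases used as intended, a link that no section makes. It also gives every spare place to failed introductions, although section 10.1 assigns them to attrition, including non-use and participants unavailable for follow-up.

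The MACE conclusion is unaffected under any reading.

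**What to change.** - **Main denominator (10.2.2, 10.3.3).** Report DOCE, its components and POCE mainly in all participants into whom the device is introduced, the Safety Population of section 10.2.1. Count a failed or abandoned deployment, or a failed retrieval, as non-success.
- **Supplementary set.** Keep the used-as-intended set as a supplementary analysis. Fix its definition and the role that assigns it before analysis, and list the excluded participants with reasons.
- **Malfunctions (10.3.3 c).** State the denominator as all study devices introduced.
- **DOCE sentence (2.0, 4.2.2, 8.3 b, 10.3.3).** Reword it so that device-caused MACE and the vessel-dissection and stent-damage events it lists are plainly failures.

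How to class a participant whose first device fails and whose second succeeds (section 6.4 allows more than one device) is a choice for the sponsor and not part of this request.

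Cost: a wording change, with no added participants. Sections 8.3 b and d already collect DOCE and device deficiencies without a used-as-intended filter, but they do not list abandoned deployments, so the case report form should be checked to confirm that these are recorded. The reported success rate may be slightly lower, and uses outside the intended use enter the main estimate. The supplementary set answers the intended-use question.
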